### **8.2 The number of subjects planned to be enrolled**

Sample size calculations were conducted using an alpha of 5% and a power of 0.8. Calculations were based on the primary and secondary variables of interest ( $VO_2$ peak

Comparing the efficacy of cardiac rehabilitation for patients with peripheral artery disease to patients with coronary artery disease/Protocol #03

and 6MWT distance) for PAD and CAD patients. To be conservative, the largest sample size (6MWT) was selected.

Previous literature has found that patients with PAD undergoing exercise training compared to PAD patients who did not undergo exercise training had improvements in the 6MWT of 34.9m (95 % CI 25.6–44.1 m,  $P<0.00001$ ) (Parmenter et al., 2015). In contrast, patients with CAD had improvements of  $29.6\pm12$ m following exercise training (Jaureguizar et al., 2016). Clinically significant changes have been defined as 20m for the 6MWT (Perera et al., 2006). A difference of 10 meters between groups is a conservative average between what is observed in the literature and the defined clinically significant change. The sample size calculation for a power of 0.8 would be 23 participants per group. Accounting for a 20% drop out, 28 patients with CAD and 28 patients with PAD will be recruited. Statistical significance will be set at a  $P$  value of 0.05.

A sample size of 28 participants per group is powered to detect a difference of 1.6 ml/kg/min between groups for VO2peak.

8.3 Procedure for accounting for missing, unused, and spurious data.

If data variables are missing, the whole participant data set will be excluded from the main statistical analysis. If some data is available, the participant's data will be included in the intention to treat analysis.

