### 5.2 Subject exclusion criteria.

Patients with vascular aneurysms, chronic heart failure, cancer, stroke, respiratory disease, or chronic kidney disease will be excluded. Patients with foot ulcers or skin breakdowns which may impede ability to exercise will also be excluded. Patients who cannot follow instructions in English will be excluded. Patients who attend less than 70% of sessions of the weekly sessions at TRI (<10 sessions in total) will be excluded from the main analysis and included in an intention-to-treat analysis.

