## **8.0 Statistics**

### **8.1 A description of the statistical methods to be employed**

Primary analysis to determine if patients with CAD or patients with PAD have greater improvements in  $VO_2$ peak, 6MWT, WIQ, and QOL will be tested with a series of two factor 2 (time: Baseline, End) by 2 (group: PAD, CAD) analyses of variances with Tukey's Honest Significant Difference (HSD) test for post-hoc corrections. This analysis will include patients who attended  $>70\%$  of on-site cardiac rehabilitation sessions. An intention-to-treat analysis will be conducted to include patients who attended less than 70% of the cardiac rehabilitation program sessions.

The secondary hypothesis that the magnitude of responses for patients with PAD will be dependent on biological sex will be tested through conducting a 3 factor 2 (time: Baseline, End) by 2 (group: PAD, CAD) by 2 (sex: men, women) analysis of variance. In addition to determine if the magnitude of responses are dependent on clinical presentation of PAD, a 2 factor 2 (time: Baseline, End) by 2 (type: asymptomatic, post-surgical intervention, IC) analysis of variance will be conducted.

To determine if PAD patients have greater exercising heart rate, rating of perceived exertion (Borg scale), rating of pain severity (, and training volumes than CAD patients, tertiary analysis will involve independent t-tests for these variables.

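### The 28 per group supports the stated 80% power for the 6MWT only if total loss from the main analysis is 18% or less, and the 20% allowance names drop-out alone

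*Combined protocol and SAP*

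**What the plan says.** Section 8.2 sets the error rates ("Sample size calculations were conducted using an alpha of 5% and a power of 0.8") and lets the 6MWT fix the size ("To be conservative, the largest sample size (6MWT) was selected"). The target is a 10 m difference between groups in 6MWT change ("A difference of 10 meters between groups is a conservative average"). The result is "The sample size calculation for a power of 0.8 would be 23 participants per group", which is then raised: "Accounting for a 20% drop out, 28 patients with CAD and 28 patients with PAD will be recruited". Drop-out is the only loss named. Section 8.2 adds that 28 per group can detect 1.6 ml/kg/min in VO2peak.

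Three other places decide who reaches the main analysis:

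- **Attendance.** Section 8.1 limits the primary analysis by attendance ("This analysis will include patients who attended" more than 70% of on-site sessions). Section 5.2 says that those below the threshold "will be excluded from the main analysis and included in an intention-to-treat analysis".
- **Completeness.** Under section 8.3, if data variables are missing, "the whole participant data set will be excluded from the main statistical analysis". Partial data go to the intention-to-treat analysis.
- **Withdrawal.** Under section 5.3, data from participants who withdraw are discarded.

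No expected rate of low attendance or of missing data is given.

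**The concern.** There are two separate problems. First, adding 20% to the required number does not give that number back after a 20% loss. The plan's own loss rate applied to its own 28 falls short of its own 23.

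Second, the allowance and the analysis set do not match. Sections 8.1, 5.2 and 8.3 send low attenders and incomplete cases to the intention-to-treat analysis, whereas withdrawn participants' data are discarded. The protocol thus treats them as different categories, and 8.2 budgets by name for only one. Section 8.3 also does not say which variables count as missing, so on a literal reading one gap could remove a participant from every main comparison.

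As a result, 8.2 does not tell a reader how many patients the main analysis should contain. A null result from a set well below 23 per group would be read against a claimed 80% power that the set did not have.

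**Working it through.** **Inputs**

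- Difference 10 m, alpha 5%, power 0.8, allowance 20%, 28 recruited per group: section 8.2.
- Two-sided test: an assumption, since 8.2 does not say. A one-sided calculation gives 18 to 19 per group, not 23.
- SD of 6MWT change 12 m in both groups: an assumption. Section 8.2 names no SD for the calculation. The 12 is the ± figure beside the cited CAD change of 29.6 m, read here as an SD, and it reproduces the plan's number.

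**1. Reproduce the 23.** Normal approximation: n = 2 × SD² × (1.960 + 0.842)² / difference² = 2 × 144 × 7.849 / 100 = 22.6, so 23. This matches. The t-test version gives 23.6, so 24.

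**2. Reproduce the 28.**

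- 23 × 1.2 = 27.6, so 28: the stated figure.
- 23 / (1 − 0.2) = 28.75, so 29: what a 20% loss requires.
- 28 × 0.8 = 22.4, so about 22 remain.

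**3. Largest loss that still leaves 23.** 28 − 23 = 5, and 5/28 = 17.9%. Losing 6 of 28 is 21.4%.

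**4. Power at the number analysed.** Normal approximation: power = Φ(10 / (12 × √(2/n)) − 1.960). At n = 22 this is Φ(2.764 − 1.960) = 78.9%. The t-test column uses the noncentral t distribution. With two time points, the time-by-group test in 8.1 is equivalent to a t-test on change scores.

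| Analysed per group | Normal approximation | t-test |
|---|---|---|
| 24 | 82.3% | 80.7% |
| 23 | 80.7% | 78.9% |
| 22 | 78.9% | 77.0% |
| 21 | 77.1% | 75.0% |

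On either scale, going from 23 to 22 costs just under 2 points.

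**5. Larger total losses.** These rates are assumed, not taken from the documents. The normal column uses the unrounded number and the t column the whole number below it.

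| Total loss from 28 | Remaining | Normal approximation | t-test | Recruits per group to keep 23 |
|---|---|---|---|---|
| 25% | 21.0 | 77.1% | 75.0% | 31 |
| 30% | 19.6 | 74.2% | 70.5% | 33 |
| 35% | 18.2 | 71.0% | 68.0% | 36 |
| 40% | 16.8 | 67.6% | 62.6% | 39 |

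**6. VO2peak.** The 1.6 ml/kg/min is stated at 28 per group, before any loss. With SD, alpha and power held fixed, the detectable difference scales with √(28/n): 1.6 × √(28/22) = 1.8 at 22.

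**7. Attendance threshold.** Sections 2.4 and 5.2 equate attending under 70% of weekly sessions with fewer than 10 sessions. Six months of weekly sessions is about 26 (assumed), and 70% of 26 is about 18. The two thresholds would exclude different numbers of patients.

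**The case against.** A reader might infer that the 80% power is simply not delivered, or that the main analysis can hold 22 per group at most. The documents do not support either reading.

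- **The inflation slip is minor.** On the normal approximation that yields the plan's 23, power is 79.6% at 22.4 and 78.9% at 22. Over both groups, 56 × 0.8 = 44.8, roughly 22 and 23 patients, with power of 79.8%. This stands.
- **22 is an expectation rounded down, not a ceiling.** The 20% is a planning rate. Losing 5 of 28 leaves the full 23. This stands.
- **Part of an apparent fall from 80% to 77% is a change of method.** At 23 the t-test already gives 78.9%. The two scales must be kept apart, as they are above.
- **The larger losses have no rates behind them.** Section 8.2 does not define drop-out, and the 20% may have been meant to cover every loss. A patient who leaves early may also fail attendance and lack month-6 data, so the exclusions can overlap. If they largely coincide, normal-approximation power stays near 79%. This stands, and it makes the conclusion conditional.
- **The SD matters more than the slip.** At 22 per group, t-test power is 84% with an SD of 11 and 70% with an SD of 13.

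None of this removes the mismatch between what 8.2 names as loss and what 5.2, 8.1 and 8.3 exclude.

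**Conclusion.** The 28 is wrong as an allowance for 20% loss (29 is needed), but that error alone costs about one patient per group and about 1 point against the 80% target on the plan's own scale. The substantive defect is that the stated 80% power for the 6MWT carries an unstated condition: total loss from drop-out, low attendance and missing data together of no more than 5 of 28 per group (18%). Whether the condition will be met cannot be judged from the documents.

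This rests on a two-sided 5% test and an SD of 12 in both groups, which together reproduce the 23. The power figures concern the 6MWT, the secondary variable that set the sample size. The primary variable is affected because its detectable difference is quoted with no loss removed.

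**What to change.** Keep 28 per group and restate 8.2 along these lines:

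> 28 per group gives 23 analysed, and 80% power for a 10 m difference in 6MWT change (SD 12, two-sided 5%, normal approximation), only if total loss from drop-out, low attendance and missing data is 18% or less. At 22 analysed per group, power is about 79% (normal approximation) or 77% (t-test).

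Add the range for larger losses, labelled as assumed: 25% to 40% total loss gives about 77% to 68% (normal approximation) or 75% to 63% (t-test). State that the 1.6 ml/kg/min for VO2peak applies to 28 analysed with no loss removed, and give it at the expected analysed number as well (about 1.8 at 22).

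Before projecting the attendance loss, reconcile the percentage and session-count thresholds in 2.4 and 5.2.

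The cost is a few sentences and a less favourable power statement. No extra recruitment is needed.

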Patients with coronary artery disease (CAD) undergoing exercise rehabilitation also have significant benefits including a lower risk for cardiovascular mortality (RR=0.74, 95%CI 0.63 to 0.87), fewer hospitalizations (RR=0.69, 95%CI 0.51 to 0.93) and improvements in functional capacity as measured by the 6 minute walk test (6MWT) ( $\Delta=60.43\text{m}$ , 95%CI 54.57 to 66.30m) (Bellet et al., 2012; Heran et al., 2011). In a prospective cohort study with 29 CAD patients undergoing cardiac rehabilitation, there was a significant improvement in  $\text{VO}_2\text{peak}$  ( $\Delta=2.45 \pm 0.5 \text{ mL/kg/min}$ ,  $P<0.001$ ) (Lucini et al., 2002). Greater improvements in  $\text{VO}_2\text{peak}$  were observed in a meta-analysis of CAD patients in cardiac rehabilitation compared to CAD patients who did not participate in cardiac rehabilitation (mean difference = 3.22ml/kg/min, 95%CI 2.42 to 4.03,  $P<0.01$ ) (Tang, Fu, Zhang, & Zhang, 2014). In spite of the results suggesting that CAD patients have greater improvements in  $\text{VO}_2\text{peak}$  following cardiac rehabilitation compared to PAD patients, there is large variability in exercise prescriptions applied limiting the strength of that conclusion.

Although a great deal of research has supported the efficacy of exercise rehabilitation for PAD, it is infrequently implemented into clinical practices (Milani & Lavie, 2007). In an analysis of the medical treatments accessed by PAD patients, exercise or diet counselling were only used in 22% of visits (Berger & Ladapo, 2017). Implementing risk factor education and exercise rehabilitation programs for patients with PAD would be consistent with the Chronic Care Model to help manage chronic diseases (Lovell, Meyers, Forbes, Dresser, & Weiss, 2011). The integration of the Vascular Clinic at the Toronto Rehabilitation Institute (TRI) will help to provide opportunities of exercise rehabilitation for patients with PAD.

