#### 3.1.1 Primary objective

The primary objective of this proposed study is to compare the magnitude of the responses to a 6-month cardiac rehabilitation program for patients with PAD in contrast to patients with CAD. The primary variable of interest will be peak oxygen consumption ( $VO_2\text{peak}$ ) with a secondary variable of interest being functional capacity, as measured by the 6-minute walk test. Tertiary variables of interest will include walking impairment, as measured by the Walking Impairment Questionnaire, and quality of life, as measured by the Short Form-36 health survey (SF-36).

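### Section 8.2 states the VO2peak detectable difference (1.6 ml/kg/min) at the 28 per group recruited, not at the roughly 22 left after its own 20% drop-out, and gives no SD from which to judge the loss of power

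*Combined protocol and SAP*

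**What the plan says.** All the sizing is in section 8.2 of the combined protocol and SAP.

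- Error rates: "Sample size calculations were conducted using an alpha of 5% and a power of 0.8".
- The walk test (6MWT) is sized for a 10 m difference between groups. The only spread given is the 12 m attached to the CAD improvement. The result is: "The sample size calculation for a power of 0.8 would be 23 participants per group".
- Allowance for loss: "Accounting for a 20% drop out, 28 patients with CAD and 28 patients with PAD will be recruited".
- VO2peak: "A sample size of 28 participants per group is powered to detect a difference of 1.6 ml/kg/min between groups". No SD and no source accompany this figure.
- The section also says that both variables were calculated and that the larger requirement, the one for 6MWT, was adopted.

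Section 3.1.1 sets the order of the outcomes: "The primary variable of interest will be peak oxygen consumption". The 6MWT is secondary.

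Three other places show who reaches the main analysis. Section 8.3: "If data variables are missing, the whole participant data set will be excluded from the main statistical analysis". Section 5.2 says that patients below the attendance threshold "will be excluded from the main analysis and included in an intention-to-treat analysis". Section 5.3 says that data from participants who withdraw are discarded.

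**The concern.** Within one section the two outcomes are put on different bases. The 6MWT figure is stated at the number needed for analysis (23) and then raised to a recruitment number (28). The VO2peak figure is stated directly at the recruitment number. The plan expects to lose a fifth of those patients and removes incomplete records from the main analysis, so it does not expect to analyse 28 per group.

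This sentence is the only power statement for the primary variable. If the comparison of VO2peak change comes out null, readers will use the 1.6 to judge which differences the study could have missed. It should therefore describe the sample that is expected to be analysed.

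**Working it through.** **Method.** The group-by-time test in a 2 x 2 analysis of variance (section 8.1) is equivalent to a two-sample t-test on change from baseline. Power is therefore taken from the noncentral t with 2n − 2 degrees of freedom and noncentrality (difference/SD) x √(n/2), at two-sided alpha 0.05. Section 8.2 does not state sidedness. Two-sided is used because it reproduces the plan's 23; one-sided gives 18 or 19.

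**1. Reproduce the plan's own number (6MWT).** Inputs: 10 m, 12 m, alpha 0.05, power 0.80.
n = 2 x (1.96 + 0.8416)² x (12/10)² = 22.6, so 23 per group, as stated.

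**2. The drop-out allowance.**
- Adding 20%: 23 x 1.2 = 27.6, so 28. This is the plan's figure.
- Keeping 23 after a 20% loss: 23/0.8 = 28.75, so 29.
- What 28 leaves: 28 x 0.8 = 22.4, so about 22 per group.

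**3. 6MWT power at what is left (10 m, SD 12 m).**

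| n per group | Normal approximation | t-test |
|---|---|---|
| 23 | 80.7% | 78.9% |
| 22 | 78.9% | 77.0% |

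**4. VO2peak.** The 1.6 cannot be reproduced, because section 8.2 gives no SD. It can only be solved backwards. The standardised difference with 80% power is 0.762 at n = 28, 0.845 at n = 23 and 0.865 at n = 22.

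*Literal reading: 80% power for 1.6 at 28 per group.*
- Implied SD = 1.6/0.762 = 2.10.
- Power for 1.6 at 22 per group: 69.5% (70.0% by the normal approximation).
- Difference with 80% power at 22: 0.865 x 2.10, about 1.8 ml/kg/min.

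*Alternative reading: 1.6 sized at 23 per group.*
- Implied SD = 1.6/0.845 = 1.89.
- Power for 1.6 at 22 per group: about 78%.
- Difference with 80% power at 22: 0.865 x 1.89, about 1.64 ml/kg/min.

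*Sized at 22:* SD = 1.6/0.865 = 1.85, and power at 22 is 80%. Any smaller sizing number implies a smaller SD and more power at 22. For all sizings at 23 or fewer, power is therefore at least 78% and the detectable difference at most 1.64.

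**5. Can the text choose between the readings?** Adopting 6MWT as the larger requirement implies that VO2peak needed 23 or fewer per group. That supports the alternative reading only if the VO2peak calculation used 1.6, which is not said. With SD 2.10, 23 per group have 80% power for 0.845 x 2.10 = 1.77. A calculation for a difference of about that size would need no more patients than 6MWT, and the same SD gives 1.6 at 28. Both sentences of section 8.2 can therefore be true under the literal reading too.

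**The case against.** The strongest reply is that no error in the 1.6 has been shown. The sentence may be exactly true of 28 patients per group, and what is missing is an SD and an evaluable number. That stands as far as it goes: the 1.6 cannot be checked, so it cannot be called miscalculated. It does not rescue the sentence as a description of this study, because the same section expects about 22 per group at analysis.

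A reader might infer that VO2peak has only 70% power. The documents do not support that. It requires 1.6 to have been solved at 28, and choosing 6MWT as the larger requirement leaves open that 1.6 was sized at 23 or fewer, in which case the loss is two points or less.

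A reader might also set the VO2peak gains cited in sections 2.1 and 7.0 against 1.6 and conclude that the study is too small for the differences it expects. That does not follow either. Those gains mix an uncontrolled before-and-after change with differences against controls, and section 2.1 itself warns that varying exercise prescriptions limit the comparison. The smallest gap that can be formed (2.45 − 1.42 = 1.03) lies below 1.6, so it is uncovered even with all 28 per group (44% power at SD 2.1). It says nothing about drop-out. Nor does the unlabelled ± 0.5 beside one CAD result in section 2.1 test the 1.6, since section 8.2 does not draw on it.

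Finally, the 6MWT shortfall is small: about two points for one patient per group. Part of the distance from 80% to 77% is only the difference between the normal approximation and the t-test. That stands.

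**Conclusion.** The point holds as a defect in how power is stated. The VO2peak figure is tied to the recruited 28 per group, while the plan's own drop-out leaves about 22. The loss of power at 1.6 ml/kg/min runs from none to two points (sized at 23 or fewer) up to about ten points (sized at 28). The difference with 80% power at 22 is at most 1.64 in the first case and about 1.8 in the second. Without the SD neither can be excluded. For 6MWT, recruiting 28 does not quite preserve the 23 required, and power at 22 is 77 to 79%.

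These figures assume a two-sided 5% test on change, equal groups and a loss of exactly 20%. The plan does not say whether the 20% also covers low attenders and incomplete records. If those exclusions come on top of it, the main analysis would have fewer than 22 per group. The finding does not show that more patients are needed.

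**What to change.** Keep 28 recruited per group and replace the VO2peak sentence in section 8.2 with one at the evaluable number:

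> With about 22 evaluable per group (28 recruited, 20% drop-out), the study has 80% power to detect a difference of X ml/kg/min in VO2peak change (SD S; X = 0.865 x S).

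Give S and its source. X is 1.6 if S is 1.85, 1.64 if S is 1.89, and about 1.8 if S is 2.1. In the same paragraph, state 6MWT power at 22 per group as just under 80%.

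The cost is wording only: recruitment and analysis do not change. The sponsor has to disclose the SD and may have to quote a slightly less favourable figure, up to about 1.8 instead of 1.6 ml/kg/min.

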## **4.0 Study Design**

### **4.1 Primary and secondary endpoints**

Patients will undergo a baseline assessment with a laboratory technician involving a standard battery of measurements and questionnaires for characteristic purposes including anthropometrics, resting blood pressure, resting heart rate, smoking status, diabetes status, current exercise regimen, and current medications. During this assessment, clinicians will review previous and ongoing medical treatment (i.e. surgical procedures, next physician visit, ankle-brachial index measurement), presence of angina, and conduct resting 12-lead electrocardiograms. This will be followed by a medical assessment by a physician to further review medical history and safety precautions for exercise. Patients will be sent home with a walking impairment questionnaire (WIQ) (McDermott et al., 1998) and a quality of life (QOL) questionnaire (SF-36) (Brazier et al., 1992) to be submitted at their next visit. A requisition for blood work will also be given to patients to be completed prior to their second visit to determine HbA1c and total cholesterol levels.

During the second visit patients will undergo a maximal cardiopulmonary exercise test to determine cardiorespiratory fitness as measured by VO2peak and will also have an exercising 12-lead electrocardiogram. The cardiopulmonary exercise test will consist of a Bruce or modified Bruce treadmill protocol (Noonan and Dean, 2000).

After determining baseline VO2peak, an individualized walking exercise prescription will be developed by a cardiac rehabilitation supervisor which corresponds to approximately 60 to 80% of VO2peak. Patients will be invited to attend weekly 90-minute supervised exercise and education sessions at the same time every week for six months, as per standard care procedures. Patients will be encouraged to gradually increase their exercise time per session as well as frequency of sessions per week.

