Clinicians at TRI will record distance walked, rest periods, exercising heart rate (as palpated by the radial pulse), ratings of perceived exertion and ratings of pain severity on a scale of 0 (no pain) to 10 (worst imaginable pain) (Hawker, Mian, Kendzerska, & French, 2011) for each exercise session at TRI. Patients will self-record their other exercise sessions on a weekly basis using standard exercise diaries. Frequency, time, type, exercising heart rate and rating of perceived exertion will be recorded for each exercise session outside of TRI. Patients will wear a non-invasive heart rate monitor (Polar) while walking at the 2nd week, 3rd month and 6th month mark of the program to help determine acute responses to aerobic exercise. Average exercising heart rate will be measured and recorded. VO2peak, 6MWT, QOL (SF-36), and walking impairment (WIQ) will be re-assessed at the 3 month and 6 month mark of the program.

Training volume will be quantified for each group for the prescribed and actual exercise load. For aerobic exercise, training will be calculated as the product of intensity in heart rate reserve, duration, and frequency for both the prescribed and actual exercise. For resistance exercise, training will be calculated as the product of weight, numbers of sets, and number of repetitions for each exercise for both prescribed and actual exercise.

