## Comparing the efficacy of cardiac rehabilitation for patients with peripheral artery disease to patients with coronary artery disease/Protocol #03

The primary endpoints of interest include change in VO2peak from month 6 to baseline, change in 6 minute walk test distance from month 6 to baseline, as well as change in walking impairment and quality of life as assessed through questionnaires from month 6 to baseline.

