### 4.6 The expected frequency and duration of study visits (anticipated time commitment) for study participants

There will be six study visits in total which coincide with standard care visits as well as the weekly visits to the cardiac rehabilitation program. Participants will not be required to make any additional visits outside of the standard cardiac rehabilitation program.

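### The plan puts participants with partial data into the intention-to-treat analysis, but the only efficacy model it names cannot use anyone without an End value on the outcome analysed

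*Combined protocol and SAP*

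**What the plan says.** Section 8.3 has two rules. For the main analysis: "If data variables are missing, the whole participant data set will be excluded from the main statistical analysis". For everyone else with something recorded: "If some data is available, the participant's data will be included in the intention to treat analysis".

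Section 8.1 compares the groups on VO2peak, 6MWT, WIQ and QOL with a series of "two factor 2 (time: Baseline, End) by 2 (group: PAD, CAD) analyses of variances", restricted to patients above the 70% attendance threshold. It describes the second analysis only by whom it adds: "An intention-to-treat analysis will be conducted to include patients who attended less than 70% of the cardiac rehabilitation program sessions". It names no model for that analysis, and no imputation or other method for incomplete outcomes appears anywhere.

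Section 4.1 defines the endpoints as changes between baseline and month 6, for example "change in 6 minute walk test distance from month 6 to baseline". It also says that all four outcomes "will be re-assessed at the 3 month and 6 month mark of the program". No analysis in Section 8.1 uses the month-3 values.

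Section 5.3 discards the data of participants who withdraw from the study. Section 4.7 separately foresees an injured participant being asked to stop the program until healed. Section 8.2 allows for 20% drop-out.

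**The concern.** The main analysis selects on something that happens after enrolment, namely attendance. The intention-to-treat analysis is the only planned check on that selection, and Section 8.3 intends it to take in people with partial data.

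The people that such a check most needs are those who stopped. Someone who leaves or pauses the program without withdrawing consent may have a baseline value, perhaps a month-3 value, and nothing at month 6. Section 8.3 counts this person in, but the only efficacy model on the page gives them no weight. If the analysis is run with that model, it adds low attenders who were measured at month 6 and leaves out those who were not. If it is run with some other method, that method is not stated and could be chosen after the data are seen.

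**Working it through.** **1. What the named model can use.** Time is measured on the same person, so the time-by-group test in a 2 (Baseline, End) by 2 (group) design is equivalent to a two-sample comparison of End minus Baseline. Without an End value there is no difference score.

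| Participant in the intention-to-treat set | Contribution to the time-by-group test for that outcome |
|---|---|
| Low attender, measured at month 6 | Yes |
| Has End on this outcome, misses another variable | Yes |
| Has Baseline, with or without month 3, but no End on this outcome | None |

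The gap is the third row only.

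**2. The plan's own sample size.** Inputs from Section 8.2: difference 10 m, 12 m taken as the SD (from the CAD figure), alpha 5% (two-sided assumed), power 0.8.

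- n per group = 2 × (1.96 + 0.84)² × 12² / 10² = 22.6, so 23, as stated.
- 23 × 1.2 = 27.6, so 28, as stated. (Dividing by 0.8 gives 28.75, so 29; the difference does not matter here.)

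**3. How many could fall in the third row.** Planned drop-out is 28 × 0.20 = 5.6 per arm, or 56 × 0.20 = 11.2 in total. The documents do not say how many drop-outs keep consent, so the whole range is shown. Every drop-out who keeps consent is taken to lack an End value.

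| Drop-outs who keep consent (assumed) | Per arm | Total | Share of consenting patients in an arm |
|---|---|---|---|
| 0% (all withdraw, data discarded) | 0 | 0 | 0% |
| 50% | 2.8 | 5.6 | 2.8 / 25.2 = 11.1% |
| 100% | 5.6 | 11.2 | 5.6 / 28 = 20.0% |

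Participants who stay in the program but miss a single month-6 measurement would add to this; no rate is given.

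**4. What month 3 would recover, at the upper bound.** Suppose that all leavers have a month-3 value and that drop-out is unrelated to outcome. In large samples, the effective number per arm for the month-6 mean change is n1 / (1 − r² × n2/n). Here n1 = 22.4 have an End value, n2 = 5.6 do not, n = 28, and r is the correlation between month-3 and month-6 change. The documents give no r, so these values are assumptions.

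| r | Calculation | Effective n per arm | Gain over 22.4 |
|---|---|---|---|
| 0.3 | 22.4 / 0.982 | 22.8 | 0.4 |
| 0.5 | 22.4 / 0.950 | 23.6 | 1.2 |
| 0.7 | 22.4 / 0.902 | 24.8 | 2.4 |

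A simulation with 22 observed and 6 missing completely at random (40,000 runs) gave about 22.9 at r = 0.5 and 24.4 at r = 0.7, against 22 for the analysis of variance. The gain is 0 if nobody keeps consent or no leaver reached month 3.

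**5. Is month 3 really measured?** Section 4.1 says so for all four outcomes. In the Section 4.6 visit list, the fifth visit corresponds to month 3. It has a 6MWT, a heart-rate strap and both questionnaires, handed out for later return, but no exercise test. Month-3 VO2peak therefore rests on Section 4.1 alone. The list's silence does not settle the matter: the sixth visit, at month 6, shows no exercise test either, although change in VO2peak to month 6 is an endpoint.

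**The case against.** The strongest reply is that this is silence, not contradiction. Section 8.1 does not say that the intention-to-treat analysis uses the same analysis of variance, and imputation is neither specified nor excluded. That is correct, so a reader should not infer that Sections 8.1 and 8.3 are flatly incompatible. But if the analysis of variance is not meant, Section 8.3 has no method behind it, and the same edit is needed.

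A reader might also infer that nobody with partial data can enter. The documents do not support this. The models run outcome by outcome, so a participant missing only the month-6 SF-36 can still count for VO2peak and 6MWT. Nor does Section 8.3 clearly bar such participants from the secondary and tertiary analyses.

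It is also fair to say that a Baseline-End model matches endpoints defined at month 6, so leaving out month 3 is not in itself an error. Month 3 matters here only as information on people without an End value.

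Finally, the affected number may be zero, the precision gain is small, and the injury provision in Section 4.7 describes a pause rather than a departure. All of this stands. It makes the point a low-cost improvement and does not remove the gap.

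**Conclusion.** The point holds in a limited form. For a participant without an End value on the outcome analysed, Section 8.3 promises inclusion that the only named efficacy model cannot give, and no alternative is stated. Those affected number between 0 and about 11 of 56 under the planned drop-out; the documents do not say where in that range the trial will fall. The recoverable precision is at most about 0.4 to 2.4 effective patients per arm for assumed correlations of 0.3 to 0.7, and less if some leavers never reached month 3.

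A reader might go further and infer that the PAD-CAD comparison is biased. That would need drop-out rates by arm and a link between drop-out and response, and the documents give neither. The main analysis of attenders is not touched by this point. The gain from acting is mainly that the inclusion rule is honoured with a method fixed in advance, in the only planned check on an attendance-selected result.

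**What to change.** In Sections 8.1 and 8.3, state that the intention-to-treat analysis is a repeated-measures mixed model on Baseline, month 3 and month 6, with the group-by-time contrast tested at month 6. Include every consenting participant with any outcome data. Report the number without an End value by arm and outcome.

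Confirm whether the exercise test is done at month 3. If it is not, the VO2peak model uses Baseline and month 6 only, and the month-3 gain applies to 6MWT, WIQ and SF-36.

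**Cost.** A few sentences in the plan and no measurement beyond those that Section 4.1 already schedules. The downside is reliance on a missing-at-random assumption that the data cannot verify; say so in the plan.

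**Optional, and not part of the core fix.** The protocol could state that stopping or pausing the program is not withdrawal from the study, and could request month-6 questionnaires by post or telephone from consenting leavers (about 15 minutes for both). Section 4.6 says "Participants will not be required to make any additional visits outside of the standard cardiac rehabilitation program", which does not forbid voluntary contact. This would need a protocol and consent amendment, and the questionnaires would recover neither VO2peak nor 6MWT.
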